12.2 Pharmacogenetics

Not applicable.

12.3 Biomarkers

Not applicable.

12.4 PK/PD

Not applicable.

13 Safety evaluation

Summaries may be performed separately for initial (Week 1-16) and entire treatment periods. The analyses of the follow-up period will be limited to summaries for treatment-emergent adverse events, serious adverse events and risks based on adverse events.

Safety analyses will be performed on treatment received or actual treatment as described below:

The actual treatment or treatment received for summaries of safety data will differ to the treatment assigned at randomization only if a subject received the wrong treatment during the entire study.

For those subjects who received not the treatment randomized, i.e. who received erroneously the wrong treatment at least once, an additional AE listing will be prepared displaying which events occurred after the treatment errors.

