3.1 Study design

This multicenter study uses a randomized, double-blind, placebo-controlled, parallel-group design. A screening (SCR) period running up to 10 weeks before randomization will be used to assess eligibility, followed by 52 weeks of treatment.

[figure not shown]
At baseline, patients will be randomized to one of the two treatment groups:

- **Group 1: 300 patients**, secukinumab 150 mg (1 mL, 150 mg/mL) s.c. PFS at BSL, Weeks 1, 2, and 3, followed by administration every four weeks starting at Week 4
- **Group 2: 150 patients**, placebo (1 mL) s.c. PFS at BSL, Weeks 1, 2, 3, 4, 8, and 12, followed by secukinumab 150 mg (1 mL, 150 mg/mL) administration every four weeks starting at Week 16

The patients will be stratified at randomization according to the region (China and non-China). Approximately 80% of randomized patients will be from China (360 Chinese patients) in order to evaluate the efficacy and safety in this patient population. No more than 30% TNF α Inhibitor Incomplete Responders (TNF-IR) patients will be enrolled in the study.

Starting at Week 16, all patients will switch to open-label secukinumab 150 mg, including all placebo patients; however, all patients and investigators/site staff will remain blinded to the original randomized treatment group assignment (150 mg vs placebo). Study treatment will continue up to Week 48.

An end of treatment visit is to be done 4 weeks after last study treatment administration and a post treatment follow-up visit is to be done 12 weeks after last study treatment administration for all subjects (regardless of whether they complete the entire study as planned or discontinue prematurely).

Figure 3-1 **Study design**

Subjects will be instructed in detail how to self-administer the s.c. injection using PFS. Each injection will be administered into an appropriate injection site of the body (thighs, arms, or abdomen). All injections will be performed at the study site. Site personnel may administer the injections to subjects who are not able to, or feel insecure to self-administer (see [Section 5.5.4](#) for more details).

Rescue medication is not allowed until Week 20 (see [Section 5.5.6](#) for more details). However, subjects who are deemed by the investigator not to be benefiting from the study treatment based on safety and efficacy assessments or for any reason of their own accord will be free to discontinue participation in the study at any time.

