Taking into account the available safety data for the individual risks outlined in the IB, the expected risk profile of secukinumab from a mechanism of action perspective is anticipated to be similar compared with other approved cytokine-targeting therapies. In some trials, infections were numerically higher in the secukinumab treatment groups than in the placebo cohorts, although no dose-dependent increase in rates of serious infections was observed. This indicates that there may not be a direct exposure related effect on host defense. The safety data from the completed studies do not suggest any unexpected safety risk of concern or any particular pattern of event clustering other than those outlined in the IB. From the standpoint of the overall risk benefit assessment, the current trial with secukinumab is justified.

4 Population

The study population will be comprised of patients (≥ 18 years old at the time of consent) with moderate to severe AS who fulfill the modified New York criteria for ankylosing spondylitis (described in Appendix 3) with prior documented radiological evidence (x-ray or radiologist's report).

Patients must have a history of active AS and report active disease as measured by the following three assessments:

- total BASDAI ≥ 4 on a scale of 0-10
- spinal pain as measured by BASDAI question #2 ≥ 4 cm (0-10cm)
- total back pain as measured by visual analog scale (VAS) ≥ 40 mm (0-100 mm)

This is a global study and it is expected that approximately 450 subjects will be randomized. Approximately 80% of randomized patients will be from China (360 Chinese patients) in order to evaluate the efficacy and safety in this patient population. A screening failure rate of 30% and post-randomization drop-out rate of 10% at primary endpoint are anticipated. Enrollment will stop as soon as the target number of randomized subjects is reached. No more than 30% TNF-IR patients will be enrolled in the study.

Patients can be re-screened only once and no study-related re-screening procedure should be performed prior to written re-consent by the subject. Mis-randomization occurs when a subject who does not meet all eligibility criteria receives a randomization number in IRT in error; mis-randomized patients will be treated as screen failures and will not be re-screened.

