- Placebo regimen: placebo (1 mL) s.c. PFS at BSL, Weeks 1, 2, 3, 4, 8, and 12, followed by secukinumab 150 mg (1 mL, 150 mg/mL) administration every four weeks starting at Week 16

Note that the treatment groups above for a subject may differ depending on the time period of the analysis and whether one assesses the subject for efficacy or safety.

Furthermore, additional aspects of efficacy, safety and tolerability of secukinumab will be investigated.

Comparative efficacy data

Comparative efficacy analyses (i.e. inferential efficacy comparisons with placebo) will focus on the time period when both active drug and the placebo are given in a manner suitable for making comparisons (e.g. double-blind). For AIN457F2308 this is the first 16-weeks of treatment. Comparative efficacy will be performed based on the FAS population using the randomized treatment. Data collected after Week 16 will generally be summarized descriptively on the FAS population using treatment sequence.

Efficacy data following treatment switch

Data will also be presented after Week 16, by a combination of the ‘original’ and ‘switch’ treatment groups and will be referred to as treatment sequence. These treatment sequences represent the treatment combinations the subjects experience over the course of the entire trial in case of switch (e.g., placebo patients who are reassigned to 150 mg secukinumab at Week 16).

4 All listings will be presented by treatment sequence. Subjects and treatments

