4.1 Analysis sets

The following analysis sets will be used in this trial:

Randomized set: The randomized set will be defined as all subjects who were randomized. Unless otherwise specified, mis-randomized subjects (mis-randomized in IRT) will be excluded from the randomized set.

Mis-randomized subjects are defined as those subjects who were mistakenly randomized into the IVR prior to the site confirming all eligibility criteria had been met and to whom no study medication was given. Mis-randomized patients are treated as screen failures.

Full analysis set (FAS): The FAS will be comprised of all subjects from the randomized set to whom study treatment has been assigned. Following the intent-to-treat principle, subjects will be evaluated according to the treatment assigned to at randomization, but actual stratum, if stratified randomization is used.

Safety set: The safety set includes all subjects who took at least one dose of study treatment during the treatment period. Subjects will be evaluated according to treatment received.

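### SAP Section 13's whole-study test for treatment received cannot reclassify a patient misdosed at every blinded dose who continues past Week 16

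*SAP*

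**What the plan says.** SAP 4.1 (and Protocol 9.1) defines the safety set without any threshold: "Subjects will be evaluated according to treatment received". SAP Section 13 then adds one. Actual treatment is to differ from randomised treatment "only if a subject received the wrong treatment during the entire study".

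The arms differ only in the first part of the trial. Protocol 3.1 states: "Starting at Week 16, all patients will switch to open-label secukinumab 150 mg, including all placebo patients". SAP Section 3 describes the placebo regimen in the same way: "placebo (1 mL) s.c. PFS at BSL, Weeks 1, 2, 3, 4, 8, and 12, followed by secukinumab 150 mg".

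SAP Section 13 also says: "Summaries may be performed separately for initial (Week 1-16) and entire treatment periods". Table 13-1 lists Day 1 to Week 16 as its own analysis period, with crude incidence only.

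For subjects "who received erroneously the wrong treatment at least once, an additional AE listing will be prepared displaying which events occurred after the treatment errors". SAP Section 9 also tabulates the numbers of active and placebo injections by treatment group.

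**The concern.** A test spanning the whole study suits a trial whose arms differ throughout. Here they differ only up to the Week 16 dose, and from then on secukinumab is the right treatment for everyone. A patient whose blinded doses were all wrong, and who goes on to Week 16, then starts to receive correct doses and so no longer meets the condition.

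That patient's 16-week adverse events are counted under a treatment the patient did not take. The Day 1 to Week 16 comparison is the only placebo-controlled safety evidence in the trial, and it has no exposure-adjusted table alongside it. A placebo-randomised patient on secukinumab throughout would put on-drug events in the placebo column. A secukinumab-randomised patient on placebo throughout would put off-drug experience in the secukinumab column. Both errors pull the columns together. For a rare serious event, the placement of one patient can change how the table reads.

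**Working it through.** The plan states no figure for this rule, so there is nothing to reproduce. The check is a count of doses, followed by the effect on the table.

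**Inputs**
- Blinded doses: baseline and Weeks 1, 2, 3, 4, 8, 12, i.e. 7 (SAP Section 3, Protocol 3.1).
- Doses from Week 16, every four weeks: Weeks 16, 20, 24, 28, 32, 36, 40, 44, 48, i.e. 9. The end point is from Protocol 3.1: "Study treatment will continue up to Week 48". Total 7 + 9 = 16.
- Planned arms: 300 secukinumab, 150 placebo.
- Drop-out, from Protocol Section 4: "post-randomization drop-out rate of 10% at primary endpoint are anticipated".

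**Step 1: can the condition be met?** Only blinded doses can be wrong in the sense of belonging to the other arm. The largest possible share of wrong doses is (blinded doses taken) / (all doses taken).

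| Last dose | Wrong / taken | Share |
|---|---|---|
| Week 4 | 5/5 | 100% |
| Week 8 | 6/6 | 100% |
| Week 12 | 7/7 | 100% |
| Week 16 | 7/8 | 87.5% |
| Week 20 | 7/9 | 77.8% |
| Week 48 | 7/16 | 43.75% |

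The condition can be met with a last dose at Week 12 or earlier, and not once the Week 16 dose is given. Where treatment ends after Week 16 makes no difference to this.

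**Step 2: how many patients are beyond the rule's reach?** At 10% drop-out, 0.10 × 450 = 45 patients leave before the primary endpoint, and 450 − 45 = 405 (90%) continue. None of the 405 could be reclassified on the dose-by-dose reading. This counts patients to whom the rule could not apply; it does not estimate how many are misdosed.

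**Step 3: effect on the 16-week table.** Let the true incidence be pP on placebo and pS on secukinumab, and let k placebo-randomised patients receive secukinumab at every blinded dose but stay in the placebo column.

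- Tabulated placebo incidence = [(150 − k)·pP + k·pS] / 150
- Tabulated difference = pS − that = (pS − pP)·(1 − k/150)

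The difference shrinks by the fraction k/150, whatever the incidences: 1/150 = 0.7%, 3/150 = 2.0%, 5/150 = 3.3%. In the other direction, m secukinumab-randomised patients wholly on placebo shrink it by m/300, by the same algebra.

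As an illustration with assumed incidences of 20% and 30% and k = 3, tabulated placebo incidence is (147 × 0.20 + 3 × 0.30)/150 = 20.2%. The 10-point difference becomes 9.8 points.

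**The case against.** **The rule can still operate.** A reader might infer that it can never reclassify anyone. The documents do not support that: a patient who stops at Week 12 or earlier can have had only wrong doses and would be moved.

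**The wording may refer to regimens.** SAP Section 3 defines the groups as regimens, and SAP 4.2 defines treatment sequences. A placebo-randomised patient on secukinumab from baseline to Week 48 followed the other regimen throughout, so the condition could be said to be met. SAP Section 3 also notes that a subject's group may differ with the analysis period. This is a fair reading, but SAP 4.2 labels randomised treatment simply as AIN457 150 mg or placebo, and Section 13 does not say which sense applies. Two programmers could place the same patient in different columns, so the wording needs settling on either reading.

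**Errors would be visible.** The extra listing and the injection counts would show them. That stands, but neither moves a patient from one column of the tables to the other.

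**Keeping partly misdosed patients as randomised is an acceptable convention.** It is evidently what the rule intends. A reader might want any secukinumab taken by a placebo patient before Week 16 counted under secukinumab. The SAP's allowance for appearing in more than one group gives exposure-adjusted rates over the entire period as its example. In a crude 16-week table, one patient would sit in two denominators with shortened observation in each, and a rule for placebo patients alone would treat the arms unequally.

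**The triggering case is unlikely.** Packs are uniquely numbered and assigned through IRT (Protocol 5.3 and 5.5.2), and every blinded dose would have to be wrong. This stands and bears on the size of the problem.

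**Conclusion.** The point holds as a minor correction. On a dose-by-dose reading, the Section 13 condition misfits the design. A patient wrong at every blinded dose who continues past Week 16 is tabulated for Day 1 to Week 16 under the arm not received, which conflicts with SAP 4.1. On a regimen reading, the rule is ambiguous.

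The expected effect is a proportional shrinkage of k/150 in the between-arm difference. This assumes 150 placebo patients, and that misdosed patients have the incidence of the drug they actually took. The documents give no value for k, and it may be zero.

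A reader might take 1/150 = 0.67 percentage points as the distortion per patient. That is an upper bound: it requires the patient to have the event and that the event would not have occurred on placebo. With an assumed true difference of 10 points, the expected distortion for k = 1 is 10 × 1/150 = 0.07 points. A reader might also infer that the rule turns the whole safety analysis into an as-randomised one, or that it hides differences. Nothing in the documents suggests errors frequent enough for that, and patients who stop before Week 16 are still handled by treatment received.

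**What to change.** Replace the whole-study condition in SAP Section 13 with one tied to the analysis period:

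- For Day 1 to Week 16 summaries, treatment received differs from randomised treatment if every dose the patient took before the Week 16 dose was the wrong treatment, in either arm.
- The same assignment carries into treatment labels and exposure for entire-period summaries. A placebo-randomised patient wholly given secukinumab is labelled AIN457 150 mg. A secukinumab-randomised patient wholly given placebo before Week 16 is labelled Placebo – AIN457 150 mg, with exposure split at the Week 16 dose as for the planned switch.
- Partly misdosed patients stay in the randomised group and appear in the adverse event listing already planned.

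The cost is a sentence or two in the SAP and a small change to the actual-treatment derivation. No extra data are needed. Settling it before unblinding avoids choosing a patient's column with the treatment codes known.

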13.1 Adverse events

The crude incidence of treatment emergent adverse events (i.e. events started after the first dose of study treatment or events present prior to the first dose of study treatment but increased in severity based on preferred term and on or before last dose date + 84 days) will be summarized

by primary system organ class and preferred term. Confidence intervals for the crude rate will be derived as described in [Section 16.2.4.1](#). In addition, exposure time-adjusted incidence rates including 95% confidence intervals will be provided for the entire treatment period (see [Section 16.2.5.1](#)). A graphical display of the crude incidence rates and exposure-adjusted rates will be presented for all AEs and serious AEs by system organ class.

Adverse events reported will be presented in descending frequency according to its incidence in the secukinumab group starting from the most common event. Summaries (crude incidences only) will also be presented for AEs by severity and for study treatment related AEs. If a particular AE 'severity' is missing, this variable will be listed as missing and treated as missing in summaries. If a subject reported more than one adverse event with the same preferred term, the adverse event with the greatest severity will be presented. If a subject reported more than one adverse event within the same primary system organ class, the subject will be counted only once with the greatest severity at the system organ class level, where applicable.

Separate summaries will be provided for adverse events suspected to be related to study drug, deaths, serious adverse events, and adverse events leading to discontinuation and adverse events requiring concomitant medication.

Separate summaries will be provided for SAEs and significant AEs that led to treatment discontinuation or dose adjustment or interruption by site in China.

Adverse events will also be reported separately by SMQ according to MedDRA, using a narrow search. The MedDRA version used for reporting the study will be described in a footnote.

A listing of non-treatment emergent adverse events will be provided. These adverse events occurred before the first dose of the study treatment. The crude incidence rate will be provided without treatment information.

For SAEs occurred during screening a listing will be prepared for all subjects screened including screening failures.

When adjudication is required of major cardiovascular events, a summary of those types of events as reported by the investigator and confirmed by adjudication will be provided.

An overview of the safety analyses which will be performed for treatment emergent AEs, labs, ECG and vital signs for each analysis period is described in [Table 13-1](#).

Table 13-1 Overview of analyses on some safety endpoints

Analysis period	AEs & SAEs	AEs by severity	Study drug related AEs	AEs-SMQ	Risk	Notables for (vitals/ECG), lab criteria
Day 1 – Week 16	• crude incidence	• crude incidence	• crude incidence	• crude incidence	• crude incidence	• crude incidence
Entire Treatment	• crude incidence • exposure time adjusted incidence	• crude incidence	• crude incidence	• exposure time adjusted incidence	• crude incidence • exposure time adjusted incidence	• crude incidence

Exposure-adjusted incidence rates will be done for the following:

- at the PSOC for AE and SAE and Level 1 for Risks and SMQ analyses

Analysis period	AEs & SAEs	AEs by severity	Study drug related AEs	AEs-SMQ	Risk	Notables for (vitals/ECG), lab criteria
-----------------	------------	-----------------	------------------------	---------	------	---

- at the PT level for common AEs, which is defined as at least 2% of the patients in the AIN457 group during the initial treatment period or events that had an incidence rate of at least 5.0 cases per 100 subject-years in the AIN457 group during the entire treatment period

If adjudication is performed, the adjudication events (myocardial infarction, stroke, and cardiovascular death) will be listed.

Algorithms for date imputations will be provided in Programming Datasets Specifications.

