9.5.3 Safety variables

9.5.3.1 Adverse events

Treatment-emergent adverse events (events started after the first dose of study treatment or events present prior to the first dose of study treatment but increased in severity based on preferred term on or before last dose + 84 days) will be summarized overall and in the Chinese population.

AEs will be summarized by presenting, for each treatment group, the number and percentage of subjects having any AE, having an AE in each primary system organ class and having each individual AE (preferred term). Summaries will also be presented for AEs by severity and for study treatment related AEs. If a subject reported more than one adverse event with the same preferred term, the adverse event with the greatest severity will be presented. If a subject reported more than one adverse event within the same primary system organ class, the subject will be counted only once with the greatest severity at the system organ class level, where applicable. Serious adverse events will also be summarized.

These summaries may be presented separately by study periods.

As appropriate, the incidence of AEs will be adjusted by treatment exposure and presented per 100 subject-years of exposure.

Separate summaries will be provided for death, serious adverse event, other significant adverse events leading to discontinuation and adverse events leading to dose adjustment (including study treatment discontinuation).

A graphical display of relative frequencies within system organ classes and relative risks, as appropriate, will be presented.

If adjudication of major cardiovascular events is required, a summary of those events as reported by the investigator and confirmed by adjudication will be provided.

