4. To demonstrate that the efficacy of secukinumab 150 mg s.c. at Week 16 is superior to placebo based on the change from baseline in total Bath Ankylosing Spondylitis Disease Activity Index (BASDAI)
5. To demonstrate that the efficacy of secukinumab 150 mg s.c. at Week 16 is superior to placebo based on the change from baseline in Short Form 36 physical component score (SF-36 PCS)
6. To demonstrate that the efficacy of secukinumab 150 mg s.c. at Week 16 is superior to placebo based on the change from baseline in Ankylosing Spondylitis Quality of Life score (ASQoL)
7. To demonstrate that the efficacy of secukinumab 150 mg s.c. at Week 16 is superior to placebo based on the proportion of subjects achieving an ASAS partial remission
8. Overall safety and tolerability of secukinumab compared to placebo as assessed by vital signs, clinical laboratory values and adverse event monitoring

3 Data presentation

To support China AS submission, tables and figures will be generated for Chinese population and overall separately. Listings will be generated for overall and will be sorted by region (China and non-China), except for the listing of randomization allocation to treatment which will be sorted by the randomization number.

Summary statistics for continuous variables will include N, mean, standard deviation, minimum, lower quartile, median, upper quartile, maximum. Summary statistics for discrete variables will be presented in the number and percent of subjects in each category.

If not otherwise specified, p-values will be presented as two-sided p-values and two-sided confidence intervals will be displayed.

The default level of significance will be set to 5% (two-sided, family-wise type-I-error).

Data analyses will be presented by treatment regimen. Efficacy and safety data for the placebo-controlled period (or the entire treatment period as appropriate) will be presented by the following 2 treatment groups. Subjects may be included in more than one treatment group for some analyses (e.g. exposure-adjusted adverse events over the entire treatment period). The 2 treatment groups represent the regimens subjects will be eligible to be randomized to for the first 16 weeks of the study.

- Secukinumab regimen: secukinumab 150 mg (1 mL, 150 mg/mL) s.c. PFS at BSL, Weeks 1, 2, and 3, followed by administration every four weeks starting at Week 4

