16.2.4.2 Odds ratio and 100*(1- α)% confidence interval

For an investigational drug group with n_1 subjects at risk, independent from the control group (e.g. placebo or comparator) with n_0 subjects at risk, of whom x_1 and x_0 experience a certain event with probability π_1 and π_0 respectively, the odds ratio is estimated as

$\frac{p_1/(1-p_1)}{p_0/(1-p_0)}$ with $p_1=x_1/n_1$ and $p_0=x_0/n_0$. A conditional exact 100*(1- α)% confidence interval

can be obtained by using the SAS procedure PROC FREQ with statement EXACT OR. However, to be able to adjust for covariates odds ratios will primarily be obtained from PROC LOGISTIC.

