16.2.4.3 Risk difference and 100*(1- α)% confidence interval

For an investigational drug group with n_1 subjects at risk, independent from the control group (e.g. placebo or comparator) with n_0 subjects at risk, of whom x_1 and x_0 experience a certain event, the risk difference is estimated as p_1-p_0 with $p_1=x_1/n_1$ and $p_0=x_0/n_0$.

Exact unconditional confidence limits for the risk difference can be obtained with SAS procedure PROC FREQ and option RISKDIFF in the TABLES statement, specifying the RISKDIFF option also in the EXACT statement.

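### No adverse-event output in the SAP is assigned a between-arm estimate with an interval for the randomised 16 weeks, and the protocol's relative-risk display is not carried over

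*SAP*

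**What the plan says.** Objective 8, the same in both documents, reads "Overall safety and tolerability of secukinumab compared to placebo as assessed by vital signs, clinical laboratory values and adverse event monitoring". Protocol 9.5.3.1 follows it with one between-arm output: "A graphical display of relative frequencies within system organ classes and relative risks, as appropriate, will be presented".

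In the SAP:

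- **Graph (13.1).** "A graphical display of the crude incidence rates and exposure-adjusted rates will be presented for all AEs and serious AEs by system organ class". Relative risk is not named anywhere in the SAP.
- **Intervals (13.1).** "Confidence intervals for the crude rate will be derived as described in" Section 16.2.4.1, which is a score interval for one group's proportion. For exposure-adjusted rates, 13.1 refers to 16.2.5.1, an exact Poisson interval for one group's rate.
- **Table 13-1.** It is introduced as "An overview of the safety analyses which will be performed for treatment emergent AEs, labs, ECG and vital signs for each analysis period". Every cell in the Day 1 to Week 16 row says crude incidence and nothing more.
- **Safety Profiling Plan (SPP) risks (13.6).** Crude and exposure-adjusted incidence only.
- **Appendix.** 16.2.4.2 defines a drug-versus-control odds ratio: "However, to be able to adjust for covariates odds ratios will primarily be obtained from PROC LOGISTIC". 16.2.4.3 defines a risk difference: "Exact unconditional confidence limits for the risk difference can be obtained with SAS procedure PROC FREQ and option RISKDIFF". No output in section 13 refers to either.
- **Section 1.** Analysis follows section 9 of the protocol, and departures from it are documented. None is recorded for the relative-risk display.

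**The concern.** Placebo patients move to secukinumab at Week 16 (Protocol 3.1), so Day 1 to Week 16 is the only period with a concurrent randomised control. It is where objective 8 can be answered without confounding by time. The outputs assigned to that period give two incidences and two separate intervals. A reader can subtract the percentages, but the uncertainty of the difference is not on the page. The natural fallback is to look at whether the two intervals overlap, and that is much stricter than an interval for the difference. A real excess on secukinumab could then pass as compatible with no difference.

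**Working it through.** **1. Tracing the outputs.** Each between-arm method was followed to see whether a safety output uses it.

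| Method | Where defined | Used by section 13? |
|---|---|---|
| Single-group crude incidence and interval | SAP 16.2.4.1 | Yes, 13.1 |
| Single-group exposure-adjusted rate and interval | SAP 16.2.5.1 | Yes, 13.1 |
| Odds ratio against control | SAP 16.2.4.2 | No |
| Risk difference against control | SAP 16.2.4.3 | No |
| Relative-risk graph | Protocol 9.5.3.1 | Not mentioned |

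The placebo-adjusted rates in SAP 16.2.2.1 are for binary response variables, so they do not fill the gap.

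**2. Design inputs.** Neither document states a figure for the safety comparison. The arm sizes (300 and 150) and the two-sided 5% level come from SAP section 15. With these, the planned power reproduces. ASAS20 at 61.1% against 28.4% gives over 99.9% by Fisher's test (stated as about 99%). Partial remission at 13.9% against 4.1% gives 93.0% (stated as 92%). The point does not depend on these figures.

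**3. One worked example, with assumed counts of 27/300 and 5/150.**

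Per-arm intervals use the continuity-corrected score method of 16.2.4.1, in its standard form with z² − 2 − 1/n under the root of the lower limit. The SAP text reads + 2 there. That only pushes lower limits down, so it would make overlap slightly more common.

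- Secukinumab: 9.0%, interval 6.1 to 13.0%.
- Placebo: 3.3%, interval 1.2 to 8.0%.
- These overlap between 6.1 and 8.0%.

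For the difference by Newcombe-Wilson, take the uncorrected Wilson limits, (2np + z² ∓ z√(z² + 4npq)) / (2(n + z²)):

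- Secukinumab: l₁ = 0.0626, u₁ = 0.1278.
- Placebo: l₀ = 0.0143, u₀ = 0.0757.
- d = 0.0900 − 0.0333 = 0.0567.
- Lower = d − √((p₁ − l₁)² + (u₀ − p₀)²) = 0.0567 − √(0.0274² + 0.0423²) = 0.0567 − 0.0504 = 0.006.
- Upper = d + √((u₁ − p₁)² + (p₀ − l₀)²) = 0.0567 + √(0.0378² + 0.0190²) = 0.0567 + 0.0423 = 0.099.

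The difference is 5.7 points, 95% interval 0.6 to 9.9.

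**4. A commoner event, with assumed counts of 90/300 and 30/150.** Protocol 3.6 gives 20-30% for infections in a rheumatoid arthritis trial; the split by arm is assumed. The per-arm intervals, 24.9 to 35.6% and 14.1 to 27.5%, overlap. The Wald standard error is √(0.3×0.7/300 + 0.2×0.8/150) = 0.0420. The difference is therefore 10.0 ± 1.96 × 4.20 points, or 1.8 to 18.2. The relative risk is 1.50 (1.04 to 2.16).

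**5. How often this happens.** Binomial probabilities were summed over all outcomes at 300 and 150. All rates are assumed.

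| True rates | Per-arm intervals separate | Newcombe-Wilson interval excludes 0 |
|---|---|---|
| 10% vs 4% | 23.8% | 62.1% |
| 8% vs 3% | 16.9% | 54.0% |
| 30% vs 20% | 28% | 63% |
| 5% vs 5%, 10% vs 10% | 0.2 to 0.4% | 4.3 to 4.9% |

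**6. Which risk-difference interval.** SAP 16.2.4.3 asks for exact unconditional limits and names no test statistic. For 27/300 against 5/150, the exact one-sided p-value at zero difference, maximised over the common rate, is:

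- 0.136 if tables are ordered by the unstandardised difference, with a lower limit of about −4.3 points, so 0 is included;
- 0.020 if they are ordered by the score statistic, so 0 is excluded (0.020 < 0.025).

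Referring to 16.2.4.3 as it stands would leave the result dependent on an unstated choice.

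**The case against.** A reader might infer that the SAP has abandoned the safety comparison and holds no between-arm estimate at all. The documents do not support that. Sections 16.2.4.2 and 16.2.4.3 define an odds ratio and a risk difference in the same part of the appendix that 13.1 cites for its crude-rate intervals. Section 1 keeps section 9 of the protocol in force, so the relative-risk display is unimplemented rather than withdrawn. Table 13-1 describes itself as covering some safety endpoints, so absence from it is not proof of exclusion. What remains is that 13.1 cites the sections it uses and these are not among them, and a method attached to no output need not produce a table.

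The protocol's commitment was also limited: a graph only, where appropriate, with no between-arm interval. That is fair, and most of the request for risk differences goes beyond restoring what was promised. Discretion over where to show relative risks still does not explain leaving them out of the SAP without a record.

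Objective 8, unlike objectives 1 to 7, does not set out to demonstrate anything, and inferential comparisons are planned for efficacy only. This stands, and it is why the proposal is descriptive.

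Finally, neither document tells anyone to judge by overlap. The percentages in step 5 therefore measure a habit of reading, at assumed rates. They cannot be read as the share of safety signals this plan would miss.

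**Conclusion.** The point holds in this form: for the randomised Day 1 to Week 16 comparison, no adverse-event output is assigned a between-arm estimate with an interval, two defined methods are attached to nothing, and the protocol's relative-risk display is missing without a recorded deviation. This rests on the text alone.

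The gap is a moderate one in reporting. It does not touch the efficacy hierarchy, its type I error, data collection or any decision rule. The practical cost depends on event rates the documents do not give. At the assumed rates above 5% with a real difference, an interval for the difference excludes zero roughly two to three times as often as separate intervals fail to overlap. For rare events the gain is small in absolute terms: at an assumed 3% against 1% the Newcombe-Wilson interval excludes zero about 17% of the time, and at 2% against 0.5% about 7%.

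**What to change.** In SAP 13.1 and the Day 1 to Week 16 row of Table 13-1, add the risk difference (secukinumab minus placebo) with a two-sided 95% score-type interval, and name one method. Newcombe-Wilson is sufficient. If exact unconditional limits are preferred, amend 16.2.4.3 to say that they are based on the score statistic rather than the unstandardised difference. Label the intervals descriptive and unadjusted for multiplicity.

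Apply this to any adverse event, serious adverse events, adverse events leading to discontinuation, system organ classes, common preferred terms (as already defined with Table 13-1) and the SPP risks in 13.6. Then either restore the relative-risk display by system organ class or record its removal as a deviation from Protocol 9.5.3.1.

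The cost is a short SAP edit and extra columns in existing tables, with no new data. The downside is a large number of unadjusted intervals. Some will exclude zero by chance, which needs a footnote, and those for rare events will be imprecise.
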